During the study period (the details of which are below), participants will complete a series of questions related to self-regulation and contexts. The questions, including the momentary self-regulation questionnaire, were used in Aim 2. Participants will be asked to complete items in response to queries using mobile ecological momentary assessment (EMA); i.e., questions/questionnaires asked at a given time point outside of a laboratory setting via a mobile device. We will assess antecedent conditions prior to health risk behavior: smoking or binge eating among our smoking and binge eating samples, respectively. These antecedent conditions include mood, companionship, location, and temptation. We will offer the resources of Laddr® (a science-based behavior change intervention delivered via an interactive, self-directed mobile platform) to individuals and assess the effect of this mobile intervention system on putative targets of self-regulatory function. Laddr will also be used to deliver the EMAs to participants. Participants will use their own smartphones.

We will ask participants to respond to EMAs and to engage with the mobile intervention for 28 consecutive days. We will prompt them four times daily to inquire about health risk behavior and ask them to complete measures of self-regulation and potentially important contexts. We will send the four prompts at random times within time windows (e.g., 8–11:30 AM, 11:30 AM–3 PM, 3–6:30 PM, 6:30–10 PM). The time windows may vary based on participants' waking hours, and we will program through the software at least an hour between prompts (e.g., if a participant receives a prompt at 11 AM, he/she cannot receive another prompt until 12 PM). We will ask them to use Laddr daily to, at a minimum, update progress toward goals and complete various activities on the application that we expect will improve their self-regulation. Participants will be recommended priority therapy guides (binge eating for the binge eating sample; smoking for the smoking sample) and can also choose to engage with other guides, such as depression, anxiety, and substance use.

Participants will also be asked to use devices that allow for objective measuring of behaviors of interest. We will ask participants in the smoking sample to provide carbon monoxide (CO) samples via a breath CO meter (iCO™ Smokerlyzer®, Bedfont® Scientific Ltd.). The monitor measures breath CO in parts per million

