We will also include a limited number of tasks; namely, the same 3 putative self-regulation tasks used in the Aim 2 imaging study: (1) two stop-signal tasks that involve responding to imperative go stimuli except when a subsequent stop signal occurs, and which maps onto four of the factors related to the drift-diffusion model that emerged in our task factor space in previous aims of our project, and (2) a delay discounting task that requires choosing between hypothetical smaller-sooner or larger-later monetary rewards, which mapped onto the fifth and final factor in the task factor space from prior project work.

We will also use a movie-watching task that includes embedded food and smoking stimuli to evaluate more naturalistic responses to these stimuli. Finally, we will include a manipulation task in the scanner that includes now and later cues to food [binge eating sample], smoking [smoking sample], and neutral stimuli. This will assess the degree to which subjects can modulate their cravings in response to external cues.

Subscales at baseline and follow-up representing the 12 factors identified in the survey factor analytic space:

1. Reward sensitivity – BIS/BAS: BAS Fun Seeking (4)
2. Sensation seeking – Zuckerman Sensation Seeking Scale: Thrill and Adventure Seeking (10)
3. Financial risk-taking – DOSPERT Risk-taking Survey: Financial (6)
4. Social risk-taking – DOSPERT Risk-taking Survey: Social (6)
5. Ethical risk-taking – DOSPERT Expected Benefits Survey: Ethical (6)
6. Eating control – Three-Factor Eating Questionnaire-R18: Uncontrolled Eating (9)
7. Impulsivity – UPPS+P Impulsivity Survey: Lack of Premeditation (11)
8. Emotional control – Ten-Item Personality Inventory: Emotional Stability (2)
9. Mindfulness – Five Facet Mindfulness Questionnaire: Act with Awareness (8)

10. Goal directedness – Selection-Optimization-Compensation: Loss-based Selection (12)
11. Agreeableness – Ten-Item Personality Inventory: Agreeableness (2)
12. Risk perception – DOSPERT Risk Perceptions Survey: Health Safety (6)

Additional surveys at baseline and follow-up:

- Brief Self-Control Scale (13)
- Ten-Item Personality Inventory (6 [10 minus 4 above])
- Three-Factor Eating Questionnaire–R18 (9 [18 minus 9 above])
- Reward-based Eating Drive Scale (RED-13) (13)
- Stanford Leisure-Time Activity Categorical Item (L-Cat 2.2) (1)
- Alcohol, smoking, and drug questionnaire from Aim 1 (36)
- Demographic questionnaire from Aim 1 (24 [28 minus 4 at screening])

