 - Baseline only

- Additional for eating sample:
 - QEWP-5 (11)
 - At screening in addition to baseline and follow-up (but baseline and follow-up will ask about past month instead of past 3 months)

- Additional for smoking sample:
 - Select set of smoking questions, including from the PROMIS Smoking Initiative (6)
 - Fagerström Test for Nicotine Dependence (5 [6 minus 1 already included in alcohol, smoking, and drug questionnaire])

Tasks at baseline and follow-up:

- Stop Signal Task
- Stimulus Selective Stop Signal Task
- Delay Discounting Titration Task
- Movie-watching Task
- Manipulation Task (with now and later cues to food [binge eating sample], smoking [smoking sample], and neutral stimuli)

Ecological momentary assessment (EMA) during study period:

- Momentary self-regulation questionnaire

- Self-reported behavior of interest (binge eating for the binge eating sample; smoking for the smoking sample)
- Questions assessing daily intents and barriers
- Questions assessing contexts

The proposed baseline battery of surveys includes approximately 200 items, and the proposed follow-up battery includes approximately 175 items. The Aim 2 baseline battery included 165 items and took roughly 20 minutes to complete. We expect the Aim 4 baseline and follow-up survey batteries to take no more than 30 minutes each. The proposed baseline and follow-up tasks are estimated to take approximately 30 minutes. The tasks will be completed within the scanner and take 60-90 minutes.

Each EMA is designed to be completed in less than five minutes. The average EMA completion time in Aim 2 at Dartmouth was less than five minutes, and we plan to administer the same EMAs in Aim 4.

Data Monitoring

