self-regulation and medical regimen adherence. We will examine each relationship separately prior to examining the full mechanistic model. To examine whether context is associated with level of momentary self-regulation, we will fit several multilevel models with momentary context as a predictor of momentary self-regulation measure. In Aim 2, we have identified several challenging contexts associated with worse momentary self-regulation, and we will confirm these relationships in this treatment-seeking sample of participants. The multilevel models will include a random individual-level effect to account for the non-independence of repeated observations over the 28-day period within an individual. Additionally, the models will also include a fixed effect of time to account for changes in momentary self-regulation over the treatment period. We will also consider a random individual-level slope term if there is significant variability in this change over time between individuals. Such a change in self-regulation over time may be due to the cumulative effect of Laddr use over the treatment period. We will also test whether including an interaction between context and recent Laddr usage is significant indicating Laddr use affects the association between context and momentary self-regulation. These models will identify contextual factors associated with increased or decreased momentary self-regulation.

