The next model will examine the relationship between level of momentary self-regulation and daily medical regimen adherence. One model for each subscale of the momentary self-regulation will be fit. In each model, momentary self-regulation will be the predictor and daily medical regimen adherence (smoking abstinence for smokers and daily physical activity for overweight/obese participants with binge eating disorder) will be the outcome. These models will identify the influence of momentary self-regulation on medical regimen adherence. Together with the previous set of models, the components of a mechanistic effect of momentary self-regulation on medical regimen adherence will be estimated. If each relationship is significant, we will fit a full multi-level structural equation model to examine the indirect effect of momentary context on medical regimen adherence as well as the direct effect of context on medical regimen adherence, independent of momentary self-regulation. Bootstrapping will be used in estimating the indirect effect in the mediation model. Bootstrapping involves taking numerous pseudo-replicate samples from the dataset and using the variability in the statistic from sample to sample to construct an interval estimate conveying the direction, magnitude, and precision

of an indirect effect. This mediation model will allow us to estimate the impact of self-regulation as a mechanism for decreased medical regimen adherence in challenging contexts.

At the individual level, we wish to examine whether Laddr can influence momentary self-regulation in a positive direction and, in turn, increase medical regimen adherence. To test this hypothesis, we will examine both the effect of time in the study on momentary self-regulation via multilevel models (e.g. linear mixed-effects models) as well as the effect of various Laddr engagement metrics on momentary self-regulation. Since Laddr use is offered as an intervention during the 28-day intervention period, time in study serves as a proxy for the cumulative effect of Laddr use. Since individuals will differ in their use of Laddr during the course of the intervention period, we will also examine Laddr engagement metrics (e.g., guides read, goals tracked) in addition to time. If Laddr usage appears to influence momentary self-regulation in a positive direction, we will again fit a multi-level structural equation model to examine both the indirect and direct effects of Laddr use on medical regimen adherence.

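### The individual-level Laddr models name no baseline covariate, so between-person effects of self-chosen Laddr use are mixed with who chooses to use it

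*Combined protocol and SAP*

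**What the plan says.** The Study Design section gives Laddr to everyone ("We will offer the resources of Laddr"); no comparison group is described. The individual-level part of the Statistical Analysis Plan asks whether Laddr improves momentary self-regulation and, through it, adherence (daily abstinence in smokers, daily physical activity in the binge eating sample). It uses two exposures. The first is time in study, as a proxy for cumulative Laddr use. The second is actual use, added because uptake is expected to vary from person to person: "we will also examine Laddr engagement metrics (e.g., guides read, goals tracked) in addition to time". If use appears to improve self-regulation, a multilevel structural equation model will "examine both the indirect and direct effects of Laddr use on medical regimen adherence".

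The only adjustment terms named appear earlier, for the context models: a fixed effect of time, a possible random slope, and a person effect ("The multilevel models will include a random individual-level effect to account for the non-independence of repeated observations"). No baseline covariate is named for any model of momentary self-regulation or adherence.

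Study Assessments lists candidates, all taken at baseline and again at follow-up: the 13-item Brief Self-Control Scale and the one-item L-Cat activity measure in both samples, and the "Fagerström Test for Nicotine Dependence" in smokers.

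**The concern.** Laddr use is chosen by the participant, not assigned. Less dependent smokers, people who are already active and people with more self-control may adhere better whatever the app does, and may also use the app more or less than others. A comparison of heavy and light users then estimates a mixture of what Laddr does and who uses it. A random intercept does not separate the two: it accounts for correlation within a person, not for a person-level variable that drives both exposure and outcome.

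The same problem reaches both the path from Laddr use to self-regulation and the path from Laddr use to adherence, so it can enter the direct and the indirect effect. These are the estimates that would be read as evidence that Laddr works through self-regulation. The baseline battery runs to about 200 items. Without named covariates, adjustment could also be chosen after the results are seen.

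**Working it through.** **Plan's own figures.** Maximum observations per sample: 77 × 4 × 28 = 8,624. After 10% drop-out and 75% EMA completion: 8,624 × 0.90 × 0.75 = 5,821. Both agree with the power section. The same inputs give 77 × 0.90 = 69 people and 28 × 0.75 = 21 observed days per person. The plan's target with adequate EMA data is 50 per sample.

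**Assumed inputs.** The documents give no correlation of any baseline measure with Laddr use (r_u) or with person-level adherence (r_a), so a range of 0.2 to 0.4 for each is used. ICC = 0.45 is the middle of the plan's 0.3 to 0.6, which is stated for momentary self-regulation and applied here to adherence. Adherence is treated as continuous with total daily variance 1. The true Laddr effect is zero. The test is two-sided 5%.

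**Person-level engagement, unadjusted.**
- Variance of a person's mean adherence: 0.45 + 0.55/21 = 0.476.
- Spurious slope per SD of use: s = √0.45 × r_a × r_u.
- Standard error: √[(0.476 − s²)/(n − 2)].

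| r_a / r_u | s | SE, n = 69 | s/SE | False positives, n = 69 | n = 50 |
|---|---|---|---|---|---|
| 0.2 / 0.2 | 0.027 | 0.084 | 0.32 | 6% | 6% |
| 0.3 / 0.3 | 0.060 | 0.084 | 0.72 | 11% | 9% |
| 0.4 / 0.4 | 0.107 | 0.083 | 1.29 | 25% | 19% |

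The rates come from the noncentral t distribution with n − 2 degrees of freedom and noncentrality s/SE. Simulation with 3,000 replicates gives the same rates. Adjusted for the baseline variable in the same simulation, the slope is about 0 and the false-positive rate is 4% to 5% at n = 69.

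**Day-to-day engagement.** In a random-intercept model of daily use, with half the variation in use lying within person, the unadjusted slope is only 0.005 SD (0.3/0.3) to 0.009 SD (0.4/0.4), with 5% to 6% false positives. The problem is therefore a between-person one.

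**Precision.** Let the baseline variables explain a share R²_a of adherence and R²_u of Laddr use. The sampling variance of the Laddr slope changes by a factor of about (1 − R²_a)/(1 − R²_u):
- R²_a from 10% to 30%, R²_u = 0: 0.90 down to 0.70 (gain).
- Equal shares: 1.00 (no gain).
- R²_a = 10%, R²_u = 30%: 0.90/0.70 = 1.29 (loss).

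Worked case, r_u = 0.3 and r_a = 0.5, counting the spurious correlation 0.3 × 0.5 = 0.15 in the unadjusted variance: adjusted 0.75/0.91 = 0.824; unadjusted 1 − 0.15² = 0.9775; ratio 0.843. So 69 people give the precision of 69/0.843 = about 82.

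**The case against.** The plan is silent on covariates; it does not rule them out. Laddr use is also not purely a matter of choice: participants are asked to use it daily, are paid $2 for each day with at least 5 minutes of engagement, and persistent non-compliers may be withdrawn and replaced. This could weaken the link between baseline characteristics and use, though the documents do not show whether it does. The structural equation model is fitted only if Laddr use first appears to help self-regulation, so the rates above are not the rate at which the plan would report a false effect on adherence. All of this stands, and it is why the size is only illustrative. It does not remove the gap, and the gating path is open to the same confounding.

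Four stronger readings are tempting, and the documents do not support them.
- *Precision is certainly lost without adjustment.* Cutting residual variance by 25% would make 69 people act like 69/0.75 = 92 only if the baseline value were unrelated to Laddr use, which contradicts the reason for adjusting.
- *False-positive rates of 23% to 51%.* These follow from a single-level correlation test at n = 69 with larger assumed correlations (0.3 with use and 0.5 with adherence, up to 0.4 and 0.6). The plan specifies multilevel models, and nothing in the documents supports correlations that large.
- *No analysis uses a baseline value.* The plan compares task and fMRI results before and after the intervention.
- *Every Laddr analysis is confounded by self-selection.* Time in study runs the same for everyone. That analysis has a different weakness: no control for time trends.

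**Conclusion.** The point holds for between-person effects of Laddr engagement on momentary self-regulation and on adherence. Exposure is self-selected, there is no control arm, and suitable baseline measures are collected but not named in these models. Under assumed correlations of 0.2 to 0.4, no true effect and n = 69, the false-positive rate for person-level engagement is about 6% to 25% unadjusted and about 5% adjusted. At the weak end the inflation is negligible. The adjusted figure assumes that the confounder is fully measured, which three questionnaires cannot guarantee: motivation and reverse causation (success prompting more use) would remain. Day-to-day use within a person is little affected, but the plan does not separate the two levels, so a reader could not tell which kind of effect had been estimated. Better precision is a possible by-product, not an argument for the change. The omission is certain; its size is not. It should be corrected before analysis.

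**What to change.** State in the Statistical Analysis Plan that, in the models of Laddr engagement on momentary self-regulation and on adherence:

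1. Person-level equations adjust for the baseline Brief Self-Control Scale and one sample-specific baseline value: the Fagerström score in smokers and L-Cat in the binge eating sample. One Fagerström item sits in the alcohol, smoking and drug questionnaire, so the score must be assembled from both.
2. Each engagement metric enters as the person's mean and the daily deviation from it, with separate coefficients.
3. Engagement effects are reported as associations.

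Do not rely on adjusting for EMA completion to separate Laddr use from general compliance. Completion is measured after baseline, and the EMAs are delivered through Laddr, so the adjustment could remove real engagement or add bias.

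The covariates cost two degrees of freedom per model, and possibly slightly wider intervals if they predict use more strongly than adherence. No new data are needed. The protocol requires the full baseline battery for a participant to continue, so missing covariates should be rare.

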(ppm) based on the conversion of CO to CO₂ over a catalytically active electrode. We will ask smoking participants to provide one CO sample in the same time window each day. Smoking participants will have a goal of smoking abstinence by the end of the study, as evidenced by a CO reading of less than 4 ppm. We will ask participants in the binge eating sample to wear a physical activity tracking device (Fitbit Flex 2™), which tracks steps, distance, calories burned, active minutes, hourly activity, stationary time, and sleep. Objective measures of eating are in a nascent phase, and all participants in the binge eating sample are overweight or obese, making physical activity a suitable behavior to measure. We will ask binge eating participants to wear the activity tracker for at least 12 hours per day. We will encourage participants to use a changing criterion design to set stepped goals, in which participants set a 7-day activity criterion goal and are encouraged to increase their criterion goals in each subsequent 7-day block if they achieve the goal on at least 4 of the 7 days.

Participants in the smoking sample may use nicotine replacement medications, and we will track which participants use these medications. Potential participants taking medications for psychiatric reasons will be excluded from both samples.

All participants will be asked to complete a battery of follow-up tasks and surveys at the end of their four-week study period. Participants will be asked to return in person to the research center to undergo a 90-minute neuroimaging session. The tasks and some of the questionnaires will be administered in the scanner. Like the baseline visit, the follow-up visit is expected to take 2.5 hours (approximately 1.5 hours of scanning and one hour of practice, setup, and assessments outside the scanner). Participants will be compensated in full at the end of their study period.

Samples

This study consists of samples from two target populations: (1) persons who smoke, and (2) overweight/obese persons with binge eating disorder. The specific eligibility criteria are as follows:

Inclusion criteria:

- Age 18–50 years
- Understand English sufficiently to provide informed consent
- Use a smartphone operating system compatible with Laddr (Android

version 5.1 or higher or iOS version 10 or higher)

- Right-handed
- Normal or corrected-to-normal vision and no color blindness
- Interest in participating in an intervention to change behavior

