The research assistant plans to monitor data quality on a daily basis and report any issues to the project manager. Our study team will use an initiation application for Laddr, developed by the same team that developed Laddr, to initiate participants into the EMA portion of the study. The team will download password-protected raw data files from a website created by the Laddr developers to monitor EMA completion and Laddr usage. These files will also allow the study team to track compensation amounts for each participant. Data are uploaded to the server when the smartphone is connected to the Internet (either via cellular or WiFi). If participants do not have access to a connection, the data are stored locally on the smartphone and uploaded to the server once a connection is established.

For the overweight/obese participants with binge eating disorder, our study team will use Fitabase, a data management platform designed specifically for Fitbit data. As long as participants maintain a wireless connection (either cellular or WiFi), the sensor data are uploaded to the Fitabase server up to every 15 minutes, allowing for monitoring throughout the day. If participants do not have access to a connection, the data are stored locally on the smartphone and uploaded to the

server once a connection is established. Fitabase allows for near-real-time data monitoring.

For the smoking participants, our study team will be able to monitor whether participants have input their daily CO readings into Laddr via the same password-protected raw data files noted above regarding EMA completion and Laddr usage.

Poor compliance regarding any data source will first be addressed through reminders sent to the participant's smartphone (text message or app notification) or email address. If poor study compliance persists, the participant may be withdrawn from the study, and an additional participant will be enrolled.

Sample Size

We propose a sample size of up to 154 participants (77 individuals who smoke and 77 overweight/obese individuals with binge eating disorder) recruited from the United States, including U.S. districts and territories.

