The proposed activities are designed to identify valid and replicable assays of mechanisms of self-regulation across populations to inform an ontology of self-regulation that can ultimately inform the development/refinement of health behavior interventions of maximal efficacy and potency. Because the need to alter health-related behavior is ubiquitous across medicine, understanding the extent to which the principles of effective health behavior change, and the mechanisms by which they work, are similar or different across health conditions and settings is a critically important area of scientific inquiry. It may inform more efficient, cost-effective, and patient-centered care. This line of research may ultimately allow us to make great strides in crafting “precision medicine” approaches for a wide array of populations. Given the importance of the knowledge to be gained, the risks to the participants are reasonable, as the risks are minimal and plans for protection against these risks are in place.

Data and Safety Monitoring Plan

Consistent with best practices, the Principal Investigator ([name]) will oversee all data and safety monitoring functions (described above) to ensure the safety of participants in the proposed study and to ensure the validity and integrity of the data obtained in the study. The Principal Investigator will also regularly meet with the Project Manager, Research Assistants, and Co-Investigators to track study progress and review these monitoring procedures. The Principal Investigator will regularly oversee all aspects of the study, including participant recruitment, informed consent, data collection, data management, and data analysis procedures, as well as regularly assess the risk/benefit ratio associated with participation in the study.

The Principal Investigator will train all project staff to recognize and report any adverse event immediately to them. Adverse events involving human participants include, for example, physical injuries, worsened physical or mental health, suicidal ideation, panic attacks, and depression. Other adverse events may also include the inadvertent disclosure by research staff of confidential research information to other persons and/or to staff of criminal justice or government agencies.

In the event that such adverse events are reported to the Principal Investigator, he will immediately inform the Chairperson of the appropriate Institutional

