Review Board, who will make a decision about whether the reported event is a Serious Adverse Event (SAE) that must be reported to the National Institute on Drug Abuse (NIDA). If the Principal Investigator determines that there is sufficient evidence of an adverse event to necessitate suspension of data collection, further IRB review, modification of the protocol, or other changes, the Principal Investigator will immediately discuss this recommendation with the Chairperson of the IRB and reach a determination of whether to suspend data collection or to stop the study from proceeding. Resumption shall be based on the concurrence of the Principal Investigator, the Chairperson of the IRB, and any other relevant parties. NIDA will receive a written report within three days of any such suspension and/or resumption of data collection.

The Principal Investigator will provide an annual summary report of all adverse events to the IRB as part of the annual review and to NIDA as part of the annual Progress Report. If no adverse events have occurred, the report will state, "No adverse events affecting human participants have occurred during this project year."

Protocol Updates

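### The plan names adverse events to be reported but identifies no question that asks participants about them, so its scripted zero-event statement could not be told apart from not having asked.

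*Combined protocol and SAP*

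**What the plan says.** The Data and Safety Monitoring Plan says that adverse events "include, for example, physical injuries, worsened physical or mental health, suicidal ideation, panic attacks, and depression". Its detection route is that the Principal Investigator "will train all project staff to recognize and report any adverse event immediately to them". For the annual report to the IRB and NIDA it adds: "If no adverse events have occurred, the report will state" the sentence "No adverse events affecting human participants have occurred during this project year".

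Study Assessments lists the baseline and follow-up instruments by name, with item counts. They cover self-regulation, personality, eating, leisure activity, substance use and, for smokers, nicotine dependence. The EMA content is momentary self-regulation, the target behavior, contexts, and "Questions assessing daily intents and barriers". Study Design shows that mood is asked by EMA, as an antecedent of smoking or binge eating.

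Data Monitoring has the research assistant check data quality daily, and has raw files downloaded "to monitor EMA completion and Laddr usage" and to track payment. Under Protections Against Risk, smokers whose psychological discomfort goes beyond that of ordinary life are to be withdrawn and referred. No means of finding them is described.

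**The concern.** A report that no events occurred is a claim about occurrence. The procedures described support only a claim about what came to staff attention. For an injury or a panic attack at home during the 28 days, or for suicidal thoughts that nobody asks about, the gap between the two can be wide.

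The plan itself acknowledges physical risk from increased activity and psychological discomfort from quit attempts. These are the effects the annual statement would be read as ruling out. The IRB and NIDA would receive a flat negative with no indication of how many participants had been asked. The rule on withdrawing and referring distressed smokers has the same dependence: it operates only if the participant speaks up or staff happen to notice.

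**Working it through.** The plan states no adverse-event rate, safety precision or detection figure, so there is no safety figure to reproduce. The check is a comparison of passages, followed by an illustration.

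**1. Contacts against content**

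- In-person sessions (Study Design): 3, namely the introductory session, first scan and follow-up scan. No adverse-event question is described at any of them.
- EMA prompts (Study Design): 4 per day × 28 days = 112 per participant. This agrees with the plan's own total in Power and Sample Size Justification: 77 × 4 × 28 = 8,624, and 77 × 0.90 × 112 × 0.75 = 5,821.2 against the stated 5,821. None of the listed EMA content is identified as a safety item.
- Surveys and tasks (Study Assessments): none is identified as an adverse-event, injury, depression, panic or suicidality measure. The nearest are EMA mood and the 2-item emotional-stability subscale. Neither has a threshold or a route into the adverse-event process.
- Daily review (Data Monitoring): directed at data quality, completion, usage and compliance.

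Contents identified as adverse-event questions: 0. What remains is staff recognition and volunteered reports.

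**2. What a zero can and cannot exclude (illustration only)**

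Let *p* be the true proportion with an event and *s* the share of events that reach staff. Neither is in the documents. With zero reports among *n* participants, the one-sided 95% upper bound on *p* is (1 − 0.05^(1/n)) / s.

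- n = 77 (one sample, Sample Size section): 1 − 0.05^(1/77) = 0.0382. The bound is 3.8% at s = 1, 7.6% at s = 1/2 and 11.4% at s = 1/3.
- n = 154 (both samples): 1 − 0.05^(1/154) = 0.0193. The bound is 1.9% at s = 1 and 3.9% at s = 1/2.

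The chance of a zero report is (1 − ps)^n. For n = 77 and an assumed p of 5%:

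- s = 1: 0.95^77 = 0.019
- s = 0.5: 0.975^77 = 0.142
- s = 0.25: 0.9875^77 = 0.380

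For an assumed p of 2%, the three values are 0.211, 0.461 and 0.680.

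A zero that would be surprising under full capture becomes unremarkable as capture falls, and the plan would have no data from which to judge *s*. Two cautions apply. The figures use maximum total enrolment, whereas the scripted sentence covers one project year, and no enrolment timeline is given. Also, the plan never uses a zero count to exclude a rate; the bounds only show how much depends on capture.

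**The case against.** The strongest reply is that this is a short, self-directed app study whose risks the protocol calls low, and that spontaneous reporting is a legitimate choice. Participants can put questions to staff at any time after consent, the consent form carries contact details, anyone in significant discomfort may stop at once, and all who finish spend about 2.5 hours at the closing visit with staff trained to recognize events. All of that stands. It rules out saying that events have no way of reaching staff, or that the withdrawal-and-referral rule can never be triggered. It argues for a light remedy, but does not make a zero interpretable.

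Item wording is also not reproduced for the surveys or the EMA, so the point rests on what the listed contents are identified as, not on proof that no item touches on safety. Likewise, the plan does not say that staff ignore the content of responses; it says only what the monitoring is for.

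A reader might infer four stronger things, none of which the documents support:

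- **That a zero report would in fact mean non-ascertainment.** Some events could be noticed or volunteered, so the defensible statement is that the two cannot be told apart.
- **That observation stops just when smokers quit.** The text is "Smoking participants will have a goal of smoking abstinence by the end of the study", which is a deadline and not a quit date. Attempts may begin at any point in the 28 days.
- **That activity goals peak beyond observation.** Participants are encouraged to raise a goal only after meeting it on at least 4 of 7 days, and every block falls before the closing visit.
- **That suspension decisions rest on the annual count.** They follow from evidence of an event and immediate discussion with the IRB Chairperson.

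**Conclusion.** The point holds in a limited form. The plan names participant-experienced adverse events, relies on passive capture, identifies no listed content as asking about them, and scripts a statement of non-occurrence. Zero reports would therefore be uninterpretable, and the rule for smokers in marked distress depends largely on self-report.

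The conclusion rests on the contents as listed and needs no assumed rate. The numerical illustration (3.8% for 0 of 77 and 1.9% for 0 of 154 with full capture, rising to 7.6%-11.4% for 0 of 77 at one half to one third capture) depends on assumed capture fractions and total enrolment. It indicates the direction and rough scale of the problem, and is not an estimate.

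The change should be made because it is cheap and improves what the IRB and NIDA are told. It does not call into question the stopping process or the length of follow-up.

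**What to change.** 1. Add a short fixed adverse-event question set to the existing REDCap follow-up battery: any new or worse physical or mental health problem, any injury, the plan's own named examples, onset date and outcome. Have staff review the answers the same day at the closing visit, and route positive answers to the reporting process already in the Data and Safety Monitoring Plan.

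2. Ask the same questions of participants who withdraw or are withdrawn, when staff are in contact with them about leaving. Otherwise those who left because of an event are missed. At the 10% drop-out assumed in the power section, that is 0.10 × 77 = 7.7, or about 8 people per sample.

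3. Replace the scripted sentence with a statement that no adverse events were reported, together with the number asked, the number answering and the events found, separating solicited from spontaneous reports.

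The cost is 1-2 minutes per participant on a follow-up battery of about 175 items, more minor events to process, and staff handling of any positive mental-health answer, which needs to be arranged before the questions go live. Two limits remain. Closing-visit questions come too late to detect distress during the 28 days, and some early leavers will not be reached. A contact after the closing visit is optional and is not needed for this point.
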